**Prospective surveillance for very early hepatocellular carcinoma
(PRECAR): a study protocol for an observational multicenter cohort
trial**

NCT number: 03588442

Date:2020.4.30

Version: v1.0

Abstract

Background: Approximately 20% patients are diagnosed to hepatocellular carcinoma at early stage, when effective treatments are feasible, and benefit from curative therapeutic approaches, such as hepatic resection and liver transplantation. Biannual ultrasound is recommended for patients with cirrhosis for early diagnosis of hepatocellular carcinoma. However, limited sensitivity and false-positivity call for development of a new surveillance tool with prior accuracy. This study aims to build a biosignature to stratify high risk population for developing hepatocellular carcinoma and to diagnosis hepatocellular carcinomas at very early stage using biological signature.

Methods: This investigator-initiated, multicenter, observational, cohort trial will enroll 5000 patients with liver cirrhosis and 5000 patients with hepatitis B virus infection. Exclusion criteria include human immunodeficiency virus infection, previous diagnosis of active pulmonary tuberculosis, and pregnancy. Patients will be recruited for 1 year and follow-up investigation will be performed biannually for 3 years to collect demographic and clinical characteristics, blood samples, disease status, and outcome data. Development of hepatocellular carcinoma and overall survival are the primary endpoints, which will be contributed to the development of the biosignature for risk stratification for incidence, diagnosis at very early stage, and survival prediction. The secondary endpoints include development of non-hepatocellular carcinoma hepatic malignancy, liver resection rate, postresection survival, and relapse-free survival.

Discussion: The biosignature will be useful in clinical practice by stratifying patients with cirrhosis or hepatitis B virus infection at high risk for development of hepatocellular carcinoma and diagnosing at very early stage.

Trial registration: ClinicalTrials.gov identifier, NCTxx, first received xx, xx 2018.

Key words: liver cancer, diagnosis, early stage, observational cohort trial, biosignature, prediction model

Introduction

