Justification of inclusion criteria for a surveillance program is determined by the risk of HCC life expectancy, and cost-effectiveness.¹² Regarding absence of experimental data, the decision for patient inclusion is based on its efficacy evaluated by heterogeneous designs, indicating that the efficacy of a surveillance program is dependent to incidence of HCC. Accordingly, populations with liver cirrhosis and HBV infection are currently recommended for surveillance.¹³

Ultrasonography and serum tumor markers are the preferred tests for surveillance of HCC based on toleration, availability, non-invasiveness, and sensitivity. Ultrasonography has a reported sensitivity of 60 to 80%, whereas α -fetoprotein was approximately 60% with the most efficient cut-off (10 to 20 ng/mL).^{14,15} Combination of ultrasonography and α -fetoprotein may increase accuracy, but also increases false-positivity and cost. Regarding importance of diagnosis of HCC at early stage, there is an unmet need for a well-made surveillance model to detect early HCC with priority in accuracy and sensitivity; identification of populations at high risk before development of HCC may be ideal if high sensitivity is achieved. In addition, it may prevent up to 6 months of disease progression and improve diagnostic sensitivity, ultimately improving prognosis.

The Prospective Surveillance for Very Early Hepatocellular Carcinoma (PRECAR) trial is designed as an observational multicenter cohort trial to conduct a signature to detect and define very early HCC and individuals at high risk of HCC by analyzing genome sequencing, plasma-

free DNA sequencing, and high-throughput protein expression screening.

Methods and Design

Ethics

The PRECAR trial will be conducted in accordance with the Declaration of Helsinki and current Good Clinical Practice guidelines. The relevant ethics committee approval will be obtained before enrolment of patients. Informed consents will be obtained from all participants before enrollment.

Eligible population

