Peripheral blood samples (25 ml) will be collected from all consenting patients at first 3 follow-up (0, 6th, and 12th month), which will be used to develop a biosignature to stratify patients at high risk for development of HCC. After development of a biosignature, 20 ml of peripheral blood samples will be collected from patients at high risk for HCC at 4th to 7th follow-up for modification and validation of the biosignature.

Statistical analysis

All statistical analyses will be performed using R (<http://www.r-project.org/>) or SPSS (Chicago, IL). Cox hazards proportional model and logistic regression will be applied to screen factors for the inclusion in a biosignature. Correlation test will be performed between results of multivariate Cox and logistic regressions, and false-positive factors will be deleted. After screening covariates, receiver operating characteristic (ROC) curves will be constructed to calculate optimum threshold for setting of cut-off value to define high risk for HCC. Independent demographic and clinical prognostic factors may be combined with the biosignature to improve performance sensitivity and specificity. Predictive signatures for cirrhosis cohort and HBV infection cohort will be developed independently. A correction for multiple testing may be applied.

Discussion

The PRECAR trial will identify predictors for development of HCC and diagnosis of very early

HCC by comparing HCC cases arising from cirrhosis or HBV infection with non-HCC developing cases. To the best of our knowledge, no prospective observational cohort trial has been published with intent to develop a biosignature to stratify patients at high risk for HCC. However, a case control study with similar design (miRNA as a diagnostic tool for HCC) is ongoing in South Africa, where HIV is hyper endemic, thus the etiology of HCC is different from the PRECAR.¹⁶ In addition, ideal aim of the PRECAR trial is to successfully stratify patients who have high potential to develop HCC and carry out intensive follow-up to prevent up to 6 months of disease progression, as well as to offer curative therapeutic options at very early stage to improve prognosis.

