Surveillance for HCC has been introduced as an effective strategy to improve prognosis of patients with HCC.¹⁷ However, this field remains to be considered immature due to absence of validation of previous studies and limited accuracy that reduced cost-effectiveness. In recent years, the development of powerful tools, such as genome sequencing, plasma-free DNA sequencing, and high-throughput protein expression screening, suggests that the establishment of a biosignature could improve sensitivity and specificity of current surveillance method. The current surveillance, which is consisted of biannual ultrasonography and α -fetoprotein, reveals limited accuracy, false-positivity, and not efficient in a timely manner. Especially, these are confined to detect already-developed HCC, indicating that if HCC occurred a month after routine surveillance, the tumor will progress for 5 followed months before the next surveillance. Regarding aggressive characteristics and rapid progression, advancement of the tumor is likely to derive patient a worse candidate for curative treatments and deteriorates survival outcomes.

The biosignature developed from PRECAR trial will improve predictive and diagnostic

accuracy for HCC in settings with cirrhosis and HBV infection. During the establishment of the PRECAR biosignature, developmental process of HCC will be further elucidated and translated to improve predictive and diagnostic accuracy. We believe that the PRECAR biosignature will be useful in stratifying patients with cirrhosis or HBV infection at high risk for HCC, as well as in diagnosing HCCs at very early stage.

Trial status

The PRECAR trial is currently ongoing. Patient recruitment will be closed on 15 July 2019 with estimated participant number of 10,000 (5000 for cirrhosis cohort and 5000 for HBV infection cohort). The final analysis will be triggered after 3 years of additional follow-up for enrolled patients for validation of the PRECAR biosignature.

References

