| Physical and clinical assessment | | | | | | | |
| Height | x | | | | | | |
| Weight | x | x | x | x | x | x | x |
| Blood pressure | x | x | x | x | x | x | x |
| Body temperature | x | x | x | x | x | x | x |
| Routine blood test | x | x | x | x | x | x | x |
| Liver function test | x | x | x | x | x | x | x |
| Renal function test | x | op | op | op | op | op | op |
| Electrolyte test | x | op | op | op | op | op | op |
| Blood glucose | x | | | | | | |
| Glycosylated hemoglobin | x | | | | | | |
| Blood lipid | x | | | | | | |
| Hepatitis virus | x | | | | | | |
| HBV DNA ^a | x | x | x | x | x | x | x |
| HIV antibody | x | | | | | | |
| Serum tumor markers | x | x | x | x | x | x | x |
| Ascites ^b | op | op | op | op | op | op | op |
| INR | x | x | x | x | x | x | x |
| Ultrasonography | x | x | x | x | x | x | x |
| Contrast enhanced CT or MRI ^c | x | op | op | op | op | op | op |
| Liver hardness | x | x | x | x | x | x | x |
| Child-Pugh score | x | x | x | x | x | x | x |
| Endpoints evaluation | | x | x | x | x | x | x |
| Sample collection | x | x | x | x | x | x | x |

HBV, hepatitis B virus; HIV, human immunodeficiency virus; INR, international normalized ratio; CT, computed tomography; MRI, magnetic resonance imaging.

^arequired for patients with HBV infection.

^brequired for patients with ultrasonography results indicating ascites.

^crequired for patients with ultrasonography results indicating hepatic nodules.

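### The Discussion claims an improvement on current surveillance, but no planned analysis compares the biosignature with ultrasound plus alpha-fetoprotein or with routine clinical data

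*Combined protocol and SAP*

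**What the plan says.** The rationale is comparative. The Abstract argues that "limited sensitivity and false-positivity call for development of a new surveillance tool with prior accuracy". The Discussion defines the comparator: "The current surveillance, which is consisted of biannual ultrasonography and" alpha-fetoprotein. It says that recent technology "suggests that the establishment of a biosignature could improve sensitivity and specificity of current surveillance method", and then states an expected result: "The biosignature developed from PRECAR trial will improve predictive and diagnostic" accuracy.

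The Statistical analysis section contains these steps: Cox and logistic regression to screen factors; a correlation step between the two sets of results; a ROC step, in which "receiver operating characteristic (ROC) curves will be constructed to calculate optimum threshold for setting of cut-off value to define high risk for HCC"; optional addition of demographic and clinical factors to the signature; separate signatures for the two cohorts; and an optional multiplicity correction. The only contrast named anywhere is in the Discussion: "comparing HCC cases arising from cirrhosis or HBV infection with non-HCC developing cases".

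Table 2 schedules the comparator throughout ("Ultrasonography | x | x | x | x | x | x | x"), with serum tumor markers also at all seven visits. It does not name alpha-fetoprotein. That alpha-fetoprotein is among the markers is a reasonable inference from the Introduction and Discussion.

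**The concern.** A ROC curve for the signature alone shows how well it separates patients who develop HCC from those who do not. It does not show whether that separation exceeds what age, platelets, liver function, liver hardness, tumor markers or ultrasonography already give in the same people. These are likely to be related both to HCC risk and to the molecular measurements, so a signature could reach a respectable AUC largely by re-expressing them.

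At stake is the headline conclusion. With no in-trial benchmark, a statement that accuracy has improved would rest on published figures from other populations. The option to combine clinical factors with the signature does not fill the gap: it enlarges the score without testing whether the new part contributes.

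**Working it through.** The plan has no figure of its own to reproduce here. The 5000 patients per cohort are given without alpha, power, effect size or HCC incidence. The main check is therefore textual; the arithmetic after it is for scale.

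**Claim against analysis**

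| Claim (Abstract, Discussion) | Analysis needed | In the Statistical analysis section? |
|---|---|---|
| Better sensitivity and specificity than ultrasound plus alpha-fetoprotein | Paired difference in the same patients, with a positivity rule for the comparator | No |
| Better prediction of HCC | Gain in AUC or C-index over routine data | No; clinical factors may be added, but the gain is not estimated |
| High-risk cut-off | ROC curve | Yes |

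**How far the published figures leave the answer open**

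Inputs, from the Introduction: "Ultrasonography has a reported sensitivity of 60 to 80" percent; alpha-fetoprotein about 60%. Assumed: a patient is positive if either test is positive, and the signature has 80% sensitivity.

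- Misses overlap fully: combined sensitivity = max(US, AFP), so max(0.60, 0.60) = 60% to max(0.80, 0.60) = 80%. The signature minus current surveillance is +20 to 0 points.
- Misses independent: 1 − (1 − 0.60)(1 − 0.60) = 84% to 1 − (1 − 0.80)(1 − 0.60) = 92%. The difference is −4 to −12 points.

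The range is therefore +20 to −12 points, and negatively associated misses would push it lower still. Specificity is not in this sum, although the Introduction says that combining the tests also raises false positives.

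**How many cases a comparison would have**

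The blood collection section samples all consenting patients at months 0, 6 and 12 only; from the fourth to the seventh follow-up it samples patients at high risk. A whole-cohort paired comparison with a next-visit window therefore reaches HCC to about month 18, whereas the month-0 signature can be related to HCC over all 36 months. Cases per cohort = 5000 × (1 − exp(−rate × years)), with assumed incidence and no dropout. Half-width = 1.96 × √(0.75 × 0.25 / n), at an assumed sensitivity of 75%.

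| Assumed incidence per year | Cases to month 18 | 95% half-width, one sensitivity | Cases to month 36 |
|---|---|---|---|
| 0.5% | 37 | 14 points | 74 |
| 1% | 74 | 10 points | 148 |
| 2% | 148 | 7 points | 291 |

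For a formal paired test, n = [1.96√pd + 0.84√(pd − d²)]² / d², where pd is the proportion of discordant pairs and d the gain (assumed: two-sided alpha 0.05, power 80%, d = 0.10). For 60% against 70%:

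- fewest discordant pairs, pd = 0.10: n = 77 cases;
- independent tests, pd = 0.6 × 0.3 + 0.7 × 0.4 = 0.46: n = 359 cases.

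The month-18 counts reach the lower figure only at the highest incidence shown and never reach the upper one. This supports an estimate with an interval, not a pass/fail test.

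**The case against.** The strongest reply is that this is a development study whose stated ideal is to find high-risk patients and follow them more intensively. The Discussion notes that current tests detect only tumours already present, so ultrasound is not a like-for-like comparator for a pre-HCC risk score. That stands for the risk aim, and it is why the main remedy is incremental value over baseline data and not a contest with ultrasound. It does not rescue the claim of better diagnostic accuracy, which is made against current surveillance. The validation that the document mentions is not described as including a comparator.

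Four stronger conclusions that a reader might draw are not supported:

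- *That the claim is untestable.* The comparator data are collected. What is missing is a planned analysis.
- *That the signature would fall 4 to 12 points short.* This needs independent misses. With full overlap an 80% signature equals or exceeds the combination.
- *That ultrasound sensitivity is near 100% by construction.* Table 2 marks follow-up CT/MRI as optional, and its footnote says when imaging is required, not that it is otherwise barred. No HCC diagnostic rule is given. Only the direction of bias, in favour of ultrasound, is plausible.
- *That the signature is meant to replace ultrasound plus alpha-fetoprotein.* The documents speak of stratifying patients and improving on the current method.

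**Conclusion.** The point holds as a gap in the planned analysis. The trial is justified by an improvement on current surveillance, and none of its planned analyses would show whether there is one, against either that surveillance or routine clinical data. This rests on reading the text and needs no numerical assumption, apart from the inference that the serum tumor markers include alpha-fetoprotein.

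The size of any error cannot be stated. The span of 20 points above to 12 points below depends on an assumed 80% sensitivity and on the assumed overlap of misses, and shows only that the published figures cannot settle the matter. The endpoints and data collection are unaffected; the conclusion about improved accuracy is.

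**What to change.** Add to the Statistical analysis section, separately for each cohort:

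1. **Main change.** Pre-specify the gain in AUC or C-index, with 95% CI, when the month-0 signature is added to a base model of baseline data already collected: age, sex, platelets, liver function, liver hardness, tumor markers, and HBV DNA where measured. The outcome is HCC over follow-up. Use cross-validated or optimism-corrected estimates for both models, repeating the factor screening inside the validation, so that a fitted signature is not set against an unfairly treated base model.
2. **Secondary, descriptive.** At months 0, 6 and 12 only, report the difference in sensitivity between the cross-validated signature and ultrasound plus alpha-fetoprotein at matched specificity, with a paired 95% CI that allows for repeated visits by one patient. State the comparator's positivity rule in advance. Show the result for HCC confirmed at that visit and for HCC confirmed by the next visit. The first favours ultrasound, because follow-up CT/MRI is required only after an ultrasound nodule. The second may count new tumours as misses, and imaging at the next visit depends on ultrasound again, so it does not remove that bias. The same-visit version will draw mainly on months 6 and 12, since Table 2 schedules no endpoint evaluation at month 0.
3. **Claims.** Limit any statement of improvement to what these analyses show, and confirm that alpha-fetoprotein is among the serum tumor markers.

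The cost is plan wording and some analysis; no new visits or samples are needed. There are two downsides. Item 2 will be imprecise, because whole-cohort signature samples are not planned after month 12. The reported gain may also look less favourable than stand-alone accuracy.

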| Physical and clinical assessment | | | | | | | |
| Height | x | | | | | | |
| Weight | x | x | x | x | x | x | x |
| Blood pressure | x | x | x | x | x | x | x |
| Body temperature | x | x | x | x | x | x | x |
| Routine blood test | x | x | x | x | x | x | x |
| Liver function test | x | x | x | x | x | x | x |
| Renal function test | x | op | op | op | op | op | op |
| Electrolyte test | x | op | op | op | op | op | op |
| Blood glucose | x | | | | | | |
| Glycosylated hemoglobin | x | | | | | | |
| Blood lipid | x | | | | | | |
| Hepatitis virus | x | | | | | | |
| HBV DNA ^a | x | x | x | x | x | x | x |
| HIV antibody | x | | | | | | |
| Serum tumor markers | x | x | x | x | x | x | x |
| Ascites ^b | op | op | op | op | op | op | op |
| INR | x | x | x | x | x | x | x |
| Ultrasonography | x | x | x | x | x | x | x |
| Contrast enhanced CT or MRI ^c | x | op | op | op | op | op | op |
| Liver hardness | x | x | x | x | x | x | x |
| Child-Pugh score | x | x | x | x | x | x | x |
| Endpoints evaluation | | x | x | x | x | x | x |
| Sample collection | x | x | x | x | x | x | x |

HBV, hepatitis B virus; HIV, human immunodeficiency virus; INR, international normalized ratio; CT, computed tomography; MRI, magnetic resonance imaging.

^arequired for patients with HBV infection.

^brequired for patients with ultrasonography results indicating ascites.

^crequired for patients with ultrasonography results indicating hepatic nodules.
